Lavender aromatherapy has been associated with decreased anxiety in a variety of clinical situations, including urodynamics, percutaneous coronary intervention in an intensive care unit, preoperative patients, during facial cosmetic injections, pre-procedural for colonoscopy or esophagogastroduodenoscopy and during hemodialysis. Ozel and colleagues found that the use of lavender essential oil aromatherapy for urodynamic testing reduced anxiety in patients. There was a decrease in anxiety from baseline to catheter placement and 15 minutes post-procedure were greater in the lavender group compared to the control group. In this randomized study of healthy controls, treatment with lavender aromatherapy will significantly decrease the pain intensity associated with Office Hysteroscopy and stress/anxiety levels as measured on a visual analog scale when compared to control subjects receiving a distilled water placebo. The purpose of this study is to determine a difference in patient-reported anxiety and pain levels before, during, and after office hysteroscopy in patients given lavender aromatherapy versus placebo. Providing more opportunities for office hysteroscopy can decrease the need to perform the procedure in the Operating Room and reduce costs and patient exposure to Anesthesia. Managing anxiety and perception of pain can help improve patient experiences and increase the utility of office hysteroscopy.

5. **Specific Aims:** The purpose of this study is to determine a difference in patient-reported anxiety and pain levels before, during, and after office hysteroscopy in patients given lavender aromatherapy versus placebo.

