6. **Research Plan:** This study design is a randomized placebo control pilot trial. Women scheduled for office hysteroscopy at the UF Shands Women's Health Clinic (Medical Plaza/Springhill) will be invited to participate. For this pilot study, we will approach 40 participants to account for 25% dropout rate and we will aim to enroll 30 participants with 15 participants in the lavender group and the placebo group, respectively. Participants who meet inclusion criteria will be randomized to the aromatherapy or the placebo group after informed consent is obtained (from PI or co-investigators) and before undergoing the hysteroscopy procedure. Randomization will occur via the sealed envelope system. Participants will be given a randomly generated treatment allocation concealed within an opaque envelope. Aside from randomization to aromatherapy versus placebo, no procedures will be performed for study purposes that would not be normally performed in the clinical evaluation. Prior to starting the procedure, the clinic nurse will prepare the aromatherapy versus distilled water on a paper towel by applying two drops of each solution on a paper towel. The patients will hold the paper towel over their nose and then they will be asked to take two deep breaths. Before the physician comes in, the nurse will ask the participant to take a deep breath while holding the towel 3 inches from her face and will instruct the participant to continue to take normal breaths subsequently. It will not be possible to blind the participants or the examiner to the assigned group since the lavender oil will have a different scent than the placebo. However, the use of distilled water on the towel will allow the possibility that the deep breathing accompanying the instruction may have an effect on

reported pain and anxiety. We will be using lavender (*Lavandula angustifolia*, Aura Cacia) essential oil and distilled water for the study and placebo arms, respectively. The oil is 100% pure essential oil obtained from steam distillation of fresh flowering tops and tested for purity by gas chromatography/mass spectrometry, specific gravity, optical rotation, and refractive index. The PI will incur a minor cost of \$13.29 associated with purchasing the lavender aromatherapy from Whole Foods Market.

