Vaginoscopy approach will be utilized to perform the procedure. This avoids the use of a speculum in the vagina or tenaculum to grasp the cervix. This atraumatic technique reduces pain stimuli generated from the cervix and the vagina when using manipulating instruments. Vaginoscopy relies on hydrodilation of the cervical canal for entry of a miniaturized scope. This technique involves distending the vaginal vault with normal saline and advancing the scope to the posterior fornix. Gently pulling back until the external cervical os is visualized and then the scope is advanced into the cervical canal.

The participant will undergo the standard clinic exam in a standardized order. The participants will complete the Hospital Anxiety and Depression Survey (HADS) at baseline. The HADS is a reliable instrument for detecting states of depression and anxiety in the setting of a hospital medical outpatient clinic. This will be used to establish their baseline anxiety levels. Participants will then be asked to rate their level of anxiety and pain immediately before beginning the exam, immediately after catheter placement, and 15 min after termination of the study using a 10-point visual analog scale and the Wong-Baker pain scale. At the end, the participants will also be asked to rate their satisfaction with the visit overall on a visual analog scale. Our primary objective is to determine the change in anxiety scores on the visual analog scale from baseline to immediate post-procedure.

- Inclusion Criteria:
  - Women aged 18 and over
  - Scheduled to undergo office hysteroscopy procedure
  - Able to give informed consent
  - Able to read and write in English
  - Anxiety score > 0 on a numerical scale at baseline
- Exclusion Criteria:
  - Any contraindication to office hysteroscopy (active pelvic infection, confirmed cervical or endometrial cancer severe hypertension, or any other condition that might be worsened by an uncomfortable test)
  - Allergy to lavender oil, or any of its components
- Withdrawal Criteria
  - The patient requests terminating participation

Flow of Events:

- The Principal Investigator or Co-Investigator will approach patients who are scheduled to undergo Office Hysteroscopy at each clinical site. PI (Resident Physician) and Co-Investigator (Attending Physician).
- Participants who agree to participate will be enrolled in the study and PI/Co-Investigator will conduct informed consent with the participant.

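### The primary objective is worded as a raw change in anxiety VAS: it names no arm contrast, gives up precision unless adjusted for baseline, and its baseline rating is not secured before inhalation

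*Protocol*

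**What the plan says.** The primary outcome is fixed in one sentence of section 6 (Research Plan): the objective is to "determine the change in anxiety scores on the visual analog scale from baseline to immediate post-procedure". The sentence mentions no arms.

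The comparison between arms is stated elsewhere. Section 5 (Specific Aims) sets out to "determine a difference in patient-reported anxiety and pain levels before, during, and after office hysteroscopy in patients given lavender aromatherapy versus placebo". The hypothesis in section 4 (Background) concerns pain and anxiety "as measured on a visual analog scale when compared to control subjects receiving a distilled water placebo", and the Abstract says much the same. Section 6 opens with "This study design is a randomized placebo control pilot trial", and for numbers "we will aim to enroll 30 participants with 15 participants in the lavender group and the placebo group, respectively".

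Three items could serve as baseline anxiety:
- the HADS, which section 6 says establishes baseline anxiety;
- an eligibility score above 0 on an unspecified numerical scale;
- the first of three VAS ratings, taken just before the examination starts.

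The towel is prepared and inhaled before the procedure begins and before the physician enters. The Flow of Events list places a baseline questionnaire and the HADS before randomisation, then the towel, then the procedure, and mentions the anxiety and pain ratings last. The contents of the baseline questionnaire are not given.

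**The concern.** The sentence that defines the primary outcome should say what is compared with what. As worded, a fall in anxiety within one arm would meet it. Anxiety may well fall in both arms once the procedure is over (an inference; the protocol gives no data). Section 6 itself allows that deep breathing with the water towel may have an effect. Only the difference between arms isolates lavender.

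Two further matters follow from choosing change as the primary quantity. First, subtracting the whole baseline rating is usually not the most precise way to use it, and with 30 participants precision is scarce. A chance baseline difference also carries into the result. Second, change is only as good as its starting point. If the starting rating follows inhalation, it may already contain part of the lavender effect, which subtraction then removes.

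**Working it through.** **The plan's own figure.** The only sample-size arithmetic in the protocol is "we will approach 40 participants to account for 25% dropout rate". It reproduces: 30 / (1 − 0.25) = 40. The protocol states no alpha, power, effect size, SD or correlation, so there is no power figure to check.

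**Inputs.** n = 15 per arm (section 6). Assumed, because the protocol does not give them: equal SD s at both times, the correlation r, and an illustrative lavender effect of 0.8 SD.

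**1. Precision with a pre-treatment baseline.**
- Difference in raw change: variance = 2(1 − r)s² × 2/n.
- ANCOVA: variance = (1 − r²)s² × 2/n, times (2n − 3)/(2n − 4) = 27/26 for estimating the slope.
- Ratio ANCOVA/change = (1 + r)/2 × 27/26. For example, at r = 0.5: 0.75 × 1.0385 = 0.779.

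Confidence-interval widths also use t quantiles on 28 df (change) and 27 df (ANCOVA).

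| r (assumed) | large-sample ratio | ratio at 15 per arm | 95% CI width ratio | 30 by ANCOVA equals, by change |
|---|---|---|---|---|
| 0.3 | 0.65 | 0.68 | 0.82 | 44 |
| 0.5 | 0.75 | 0.78 | 0.88 | 39 |
| 0.7 | 0.85 | 0.88 | 0.94 | 34 |
| 0.8 | 0.90 | 0.94 | 0.97 | 32 |
| 0.9 | 0.95 | 0.99 | 0.995 | 30 |
| 0.95 | 0.975 | 1.01 | 1.01 | no gain |

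The last column is 30 divided by the unrounded ratio. The variances are equal when (1 + r)/2 × 27/26 = 1, that is r = 25/27 = 0.93.

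A simulation (20,000 trials, 15 per arm, 0.8 SD effect) agrees. Both methods average about −0.80 SD, so they target the same effect. Power for change versus ANCOVA is 44% vs 59% (r = 0.3), 57% vs 67% (0.5), 78% vs 83% (0.7) and 92% vs 94% (0.8). Within a single trial the two estimates still differ, by 0.14 SD on average at r = 0.5.

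**2. Chance imbalance.** The standard error of the baseline difference is √(2/15) = 0.37 SD. An imbalance of that size shifts the raw-change estimate by (1 − r) × 0.37, which is 0.18 SD at r = 0.5. ANCOVA removes this shift in expectation.

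**3. Baseline taken after inhalation.** Let lavender shift the first rating by b and the post-procedure rating by p. Raw change then estimates p − b, and ANCOVA on that rating estimates p − r·b.
- b = −0.4, p = −0.8: change gives −0.40; ANCOVA gives −0.8 + 0.5 × 0.4 = −0.60 at r = 0.5, and −0.68 at r = 0.3.
- b = p = −0.8: change gives 0.00; ANCOVA gives −0.8 + 0.5 × 0.8 = −0.40 at r = 0.5.

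The simulation matches these values. Neither method recovers −0.8, so adjustment alone does not cure a baseline taken too late.

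**The case against.** A reader might infer that the protocol plans no comparison between arms. It does plan one: the Abstract, Background, Specific Aims and design statement all say so, and the primary-objective sentence read alongside them plainly means change compared between arms. The gap is in that one sentence. It still matters, because the Aims cover anxiety and pain at several times and single out no primary; only the sentence without arms does.

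A reader might also infer that the protocol commits to an unadjusted change-score test. It names no test or model. A change outcome is compatible with ANCOVA, since regressing change on arm and baseline gives the same arm effect as regressing the post value. The choice of model is commonly left to the SAP, which is not at hand, so its absence is no fault. The loss in the table applies only if raw changes are compared without adjustment.

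Nor can ANCOVA be called clearly better whatever the data. The gain is substantial at low to moderate r, about 6% of variance at 0.8, about 1% at 0.9 and gone by about 0.95. The protocol does not say where r lies.

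Finally, the documents do not prove that the baseline VAS follows inhalation. The baseline questionnaire comes before randomisation and might contain a VAS. What stands is that nothing in the text secures this, while the first VAS it describes falls just before the examination, by which time the towel may have been used.

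**Conclusion.** The concern holds as a matter of definition and efficiency; it does not show an invalid design. The primary-objective sentence should carry the arm contrast that the protocol states elsewhere. Comparing raw changes at 15 per arm would have higher variance than an adjusted comparison: the adjusted variance is lower by about 32%, 22% and 12% at r = 0.3, 0.5 and 0.7, with little or no gain from 0.9 upward. These figures rest on equal SDs, an assumed r and a baseline rated before treatment.

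That last condition carries the most weight. If the baseline VAS follows inhalation, change from it could remove anything from part of the lavender effect to all of it, depending on how far lavender has already lowered that rating. The size is unknown; the values shown are illustrations.

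**What to change.** Reword the primary objective, for example:

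> The primary outcome is the difference between arms (lavender minus water) in anxiety VAS immediately after the procedure, estimated by ANCOVA with adjustment for an anxiety VAS recorded before randomisation and before inhalation, with a 95% confidence interval. Within-arm change is reported descriptively only.

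If the sponsor prefers to keep change as the outcome, the same model with change as the response gives the same arm effect, provided the baseline VAS is a covariate.

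State in section 6 and in the Flow of Events which rating is the baseline and that it precedes randomisation and the towel. Reconcile the post-procedure time point as well: the section 6 narrative lists ratings after catheter placement and at 15 minutes, while the Flow of Events lists one after the procedure and one at 15 minutes.

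The cost is small but not nil. The eligibility anxiety score must be recorded on the same VAS, or one brief rating added before randomisation. The analysis gives up one degree of freedom (27 instead of 28), already counted in the 15-per-arm ratios and interval widths.

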- Prior to starting the hysteroscopy procedure, the participants will complete a baseline questionnaire and a Hospital Anxiety and Depression Survey (HADS).
- Participants will be randomized into two groups (aromatherapy or placebo).
- Participants will hold a paper towel over their nose and take two deep breaths.
- For each group, the protocol will be the same except the towel held over the nose will be scented with lavender oil or distilled water.
- The hysteroscopy procedure will proceed under a standardized protocol that is not directly related to the study.
- Participants will be asked to rate their level of anxiety and pain immediately before, after, and 15 minutes after completing the procedure. Participants will be monitored for 30 minutes post-procedure and participation in the study will conclude at the end of this time interval.

7. **Possible Discomforts and Risks:** The risks and discomforts with this study are based on baseline risk/discomforts associated with the hysteroscopy procedure. Specifically related to the study, the risk involves exposure to Lavender oil and possible side effects associated with this exposure. We do not anticipate any significant complications associated with the procedure or the study oil. However, we will monitor the participant for at least 30 minutes post-procedure for side effects related to the oil, such as nausea, vomiting, headache, or allergic reaction. Women are given verbal and written post-op instructions by the clinic nurse upon discharge. Participants will be provided with the phone number of the clinic and PI and will be instructed to contact the clinic and/or PI should have any questions or problems.

Additional risks include breach of confidentiality. To ensure the privacy of participant information, collected data will be stored on an electronic base encrypted database (Redcap) and this will only be accessible to study staff. Any additional research documents will be saved on a password-encrypted jump drive and locked in a filing cabinet in the Minimally Invasive Gynecologic Surgery office at the Springhill or Medical Plaza office. At the completion of the study, all personal identifiers will be destroyed in a HIPAA-compliant manner.

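### Side-effect recording is tied to the period after the procedure and to effects of the oil, so brief early reactions may go unrecorded and counts by arm would not be a fair comparison (minor)

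*Protocol*

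**What the plan says.** **Exposure.** Item 6 (Research Plan) places it before the hysteroscopy: "Prior to starting the procedure, the clinic nurse will prepare the aromatherapy versus distilled water on a paper towel". The woman takes two deep breaths through the towel, then another with the towel near her face before the physician enters. The nurse then "will instruct the participant to continue to take normal breaths subsequently". No end of exposure is given.

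**Monitoring.** Item 7 (Possible Discomforts and Risks) says "we will monitor the participant for at least 30 minutes post-procedure for side effects related to the oil", with the examples "such as nausea, vomiting, headache, or allergic reaction". The Flow of Events in item 6 says "Participants will be monitored for 30 minutes post-procedure and participation in the study will conclude at the end of this time interval". No other side-effect observation is described.

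**Arms and blinding.** The trial uses "essential oil and distilled water for the study and placebo arms, respectively". Item 6 states: "It will not be possible to blind the participants or the examiner to the assigned group". The Flow of Events adds: "For each group, the protocol will be the same except the towel held over the nose will be scented with lavender oil or distilled water".

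**Aim.** Items 5 and 6 concern anxiety and pain, with overall satisfaction also rated. Tolerability is not listed as an aim.

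**The concern.** Two features of the monitoring sentence fit the exposure badly.

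- **Timing.** The stated period lies after the procedure, whereas the oil is first inhaled before it. The interval nearest to exposure has no planned recording.
- **Relatedness.** The sentence looks for effects of the oil. Item 7 itself says that hysteroscopy brings its own risks and discomforts, but it gives no rule for separating the two sources and names nobody to judge. Staff can know the arm. On a literal reading, a woman who inhaled distilled water cannot have an effect of the oil, so the same symptom could be listed in one arm and passed over in the other.

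At stake is the small amount of safety information the pilot can yield. Early reactions could be under-recorded, and an excess in the lavender arm could arise from attribution alone. The water arm could show how often these symptoms follow the procedure itself, but the wording gives staff no reason to record them there. When and in whom symptoms are recorded is fixed at data collection, and an analysis plan cannot recover what was never written down.

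**Working it through.** **Figures in the protocol.** There is none on side effects. The only calculated figure is the number to approach: 30 / (1 − 0.25) = 40, which reproduces. The one input used below is 15 women per arm (item 6). Every rate and fraction is an assumption, shown as a range.

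**Step 1: the timeline.** In the protocol's order: towel prepared, deep breaths, further breathing near the towel, physician enters, hysteroscopy, end of procedure, 30 minutes of monitoring. Both statements on monitoring (Flow of Events and item 7) refer to the last stage. Everything from the first breath to the end of the procedure has no recording attached to it.

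**Step 2: effect of the window.** Let *p* be the chance that a lavender participant reacts, and *f* the fraction of reactions that come and go before the procedure ends. If those go unrecorded, the chance of recording at least one reaction in 15 women is 1 − (1 − p(1 − f))^15.

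| p | f = 0 | f = 0.25 | f = 0.50 | f = 0.75 |
|---|---|---|---|---|
| 10% | 79% | 69% | 54% | 32% |
| 20% | 96% | 91% | 79% | 54% |

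For example, with p = 0.10 and f = 0.50: 1 − 0.95^15 = 0.537.

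**Step 3: effect of attribution.** Let *b* be the rate of procedure-related symptoms, equal in both arms, and *q* the share of them attributed to the oil in the lavender arm. Expected oil-related events are 15 × b × q with lavender and, read literally, 0 with water. The true difference is zero.

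| b | q = 25% | q = 50% | q = 100% |
|---|---|---|---|
| 10% | 0.375 | 0.75 | 1.5 |
| 20% | 0.75 | 1.5 | 3.0 |
| 30% | 1.125 | 2.25 | 4.5 |

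The apparent excess is b × q, from 2.5 percentage points (0.10 × 0.25) to 30 (0.30 × 1.00).

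**Step 4: what 15 per arm could show with complete recording.** With 0 of 15 events, the one-sided 95% upper bound is 1 − 0.05^(1/15) = 18.1%. Fisher's exact test gives p = 0.100 for 4 of 15 against 0 of 15, and p = 0.042 for 5 against 0. Any safety comparison here is coarse.

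**The case against.** The strongest reply is that item 7 is a participant-risk section. It promises observation as a precaution and defines no endpoint, count or comparison, so there is no tolerability result to bias. That largely stands, and it is why the point is minor. It does not remove the mismatch between the stated monitoring and the exposure.

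Three stronger readings are tempting, and the protocol does not support them.

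- **Early reactions are missed.** A reader might infer this from the window. But the nurse prepares the towel and coaches the breathing, and the physician then does the procedure. Nothing says that an early reaction would be ignored, and one that persists falls inside the window. The stated time can also be read as how long observation must last rather than when it opens. Only brief early reactions are at risk of going unrecorded.
- **The arms cannot be compared, because the control count is zero by definition.** That takes the relatedness phrase as a strict filter on recording. It may only name the symptoms to watch for. The Flow of Events has all participants monitored for the same time, with no limit by arm or cause. A comparison would be possible if every event were recorded. What stands is that the wording is ambiguous, and that its literal reading is one-sided in an unblinded trial.
- **The two durations conflict.** Item 7 gives a minimum of 30 minutes; the Flow of Events gives 30 minutes, after which participation ends. Thirty minutes meets that minimum, so there is no contradiction.

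It is also fair to say that the sizes above rest wholly on assumed rates, and that reporting counts by arm may be left to an analysis plan that is not shown.

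**Conclusion.** The point holds as a minor weakness in how side effects are to be recorded. The stated monitoring follows the procedure while exposure precedes it, so brief early reactions may go unrecorded. The focus on effects of the oil, with staff able to know the arm and a water control, means that any side-effect counts would not be a fair between-arm comparison.

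The direction follows from the protocol's text if the relatedness phrase governs what is written down. The size does not follow from the text. Under the assumed ranges, attribution alone gives roughly 0.4 to 4.5 expected events against 0. The upper end needs a 30% background rate with every such event blamed on the oil. Most of the range lies below the 5-against-0 split needed for p < 0.05, so the likelier harm is a misleading description than a false significant result. The anxiety and pain comparison and the planned sample size are unaffected.

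**What to change.** In item 7 and in the Flow of Events, state that nausea, vomiting, headache and allergic reaction are recorded in both arms with the same short checklist, from first inhalation to the end of the post-procedure observation, whatever the presumed cause. Enter any attribution to the oil in a separate field.

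The cost is a wording amendment and four items on the data collection form. No extra procedure or staff should be needed. The small downside is that more procedure-related events will be listed in both arms. The change concerns data recording only; it prescribes no observation time and no clinical management.
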